### **9.5.2 Key Secondary Outcome(s)**

**Functional Key Secondary Outcomes:** One key secondary objective of this study is to show greater improvement in specific standardized language, cognitive, and adaptive measures (see Endpoints Derived from Evaluations Section). To address this objective, a number of key secondary functional endpoints will be obtained (using all raw scores, except as noted):

- Mullen Scales of Early Learning (MSEL)
  - Development Quotient (DQ)
  - Expressive Language Subscore
- Vineland Adaptive Behavior Scale – Version 3
  - Composite Score
  - Communication Subscore
- Preschool Language Scale – 5th Edition
  - Expressive Communication Score
- McArthur-Bates Communication Development Index
  - Number of Spoken Words
- Clinical Global Impression-Improvement (CGI-I)
  - Overall Function

Although the primary outcome was chosen to be the likely most sensitive measure to the intervention, albeit less validated, the additional key secondary functional outcomes were chosen to be the measures most validated, accepted and utilized in the FXS population, albeit potentially somewhat less sensitive to change. This should allow exploration of both novel and sensitive strategies for measuring outcome as well as standard strategies. The secondary measures chosen will most reliably assess broad domains of cognitive, language, adaptive and maladaptive functioning. It is anticipated that gains in language will result in broader improvement in overall functioning in multiple domains, and it is possible the AFQ056 will target learning in domains outside of those covered by the language intervention, although it is hard to predict which domains will be most impacted. Thus, the mostly broadly used and well-validated general standardized measures for the cognitive, language, adaptive and maladaptive domains were chosen as key functional secondary outcomes.

The Mullen Scales of Early Learning (MSEL) has been used to track developmental progress of children with FXS in longitudinal studies and to characterize cohorts of young children with FXS for many years. More recently the MSEL was analyzed in a retrospective chart review to evaluate effects of early sertraline treatment on development in FXS and has been used in a 6 month placebo-controlled clinical trial of sertraline in young children with FXS.

The Vineland Adaptive Behavior Scale (Vineland, all editions) has been used extensively to track progress of children with FXS in large longitudinal studies and to characterize cohorts of patients with FXS both for clinical trials and other studies. The Vineland-II has been used in a phase 2 trial of arbaclofen and showed improvement in the Socialization subscore in a post-hoc analysis of the more socially impaired subgroup of FXS participants and the Daily Living subscore showed significant improvement in a recent placebo-controlled phase 2 trial of metadoxine in FXS.

The Preschool Language Scale, now on Version 5 (PLS-5), has been used to track language progress of children with FXS in longitudinal studies and to describe the language profile of patients with FXS for many years.

The MacArthur-Bates Communicative Development Inventory gives an opportunity to make sure language data is acquired even for children uncooperative with assessment, as it is a parent interview that allows tracking of the child's progress in developing words, sentences, and more complex language. This involves a parent-report measure that has been well-validated against direct observation and assessment measures of typical child language status and growth. This measure has been used to track language developmental trajectory in young children with ASD as well as other developmental disabilities, and has been shown effective in characterizing language change in populations with limited communication abilities.

The Clinician Global Impression (CGI-I) assesses clinician or caregiver impression of global functioning or a specific symptom to which the CGI-I is anchored. Collection of global clinician and parent impressions allow mapping of specific responses to more general perception of function, and give a sense of whether changes on more specific measures are meaningful. The CGI-I has been used in virtually all prior trials in FXS to assess global change in various pre-specified target behaviors or function. Standardized training modules exist for training investigators to reliability on this measure. The CGI has been sensitive to change in the ITT population in a placebo-controlled trial of minocycline in FXS and in post-hoc subgroup analyses of placebo-controlled trials of arbaclofen and AFQ056.

### 9.5.3 Other Secondary & Exploratory Outcomes

#### Safety Endpoints

The number of adverse events (AEs) and serious adverse events (SAEs) will be tracked over time. Counts will be statistically compared among the AFQ056 and placebo groups to evaluate safety in regards to whether levels are statistically equivalent over time. This will be looked at separately during the main study phase and extended study phase. In order to evaluate safety, the following will be assessed.

- Safety measures including clinically significant laboratory values and adverse events tabulated for descriptive comparison between the placebo and active drug groups.
- Tolerability, defined as the ability to at least continue treatment after the dose has been reduced to the lowest allowed dose (12.5 mg) due to side effects. The necessity to discontinue treatment after dose reduction to 12.5 mg would be considered lack of tolerability.

**Biomarker Exploratory Outcomes:** Another key secondary objective of this study is to show improvement in specific measures from ERP biomarkers in the combination of the AFQ056/language intervention group relative to those in the language intervention/placebo group. To address this objective, a number of key secondary biomarker endpoints will be obtained:

- ERP
  - Auditory habituation first 15% versus last 15% for amplitude of pediatric p50/N1 (P1) peak occurring at approximately 100 ms post-stimulus
  - Amplitude of auditory response at three components: pediatric p50/N1, N2, and P2
- Eye Tracking
  - Percent of looking time to eyes (all conditions)
  - Number of fixations to eyes (all conditions)

The major key secondary biomarker outcome was chosen as auditory habituation on ERP given the test is abnormal in FXS, it directly measures cortical activity which is what the drug is proposed to change, auditory processing is linked to language functioning, and it has shown improvement in a prior trial of minocycline. Abnormal enhanced cortical auditory responses are seen in the FXS mouse. Further, MPEP (mGluR5 NAM) was shown to reduce N1 auditory EP amplitudes in a mouse model of autism, suggesting mGluR5 involvement in modulation of this response. Habituation of N1, P2, N2 components of auditory ERP has been studied in FXS and these components were shown to be significantly enhanced in 16 males with the FXS full mutation relative to 20 age-matched controls. By focusing on the changes in the N1, P2, and N2 components (relative to the common average reference) of subject ERP signals, between the first and last 45 stimuli presented, Schneider et al. showed that there was abnormal electrocortical habituation to auditory stimuli in patients with FXS, and this improved at N1 and P2 in individuals with FXS who were given minocycline treatment compared to a control group. Data from the ERP recording will also be subjected to analyses of MMN and resting state (when obtainable) as an exploratory marker as no data currently exists on these measures in FXS.

Eye tracking was chosen as an additional key secondary biomarker outcome because it is abnormal in FXS, it corresponds well to a key phenotype of gaze aversion in FXS, it has strong feasibility and test-retest reliability, it might be expected to improve if language improves, as eye

gaze is often used to initiate communication, and most importantly, it improved in the phase IIb placebo-controlled trial of AFQ056 in adolescents and adults suggesting it is sensitive to treatment with and may provide an index of disease reversal by mGluR5 NAMs. Eye Tracking has good feasibility and reproducibility in FXS and has been used in several targeted treatment trials for older individuals with FXS.

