The study number for the subject and study visit number will be added to the label by the coordinator at each study visit when the study drug is given to the subject. Study drug will be dispensed to subjects at all study visits after screening, until the Follow Up visit, after which no more study drug will be provided. From the month 8 visit on, study drug will no longer be blinded and all subjects will receive active drug. Drug dispensed at the month 8 visit and after will be labeled as AFQ056 and will contain the same information as the AFQ056/placebo labels for bottles dispensed up to month 8. Amount of study drug dispensed during flexible dosing periods will be calculated to accommodate any possible dose increases that would occur prior to the next study visit. All bottles of study medication including empty, partially used and unused bottles will be returned to the study site at each visit, and a new set of bottles will be dispensed.

Study drug will be received at the study site by a designated person, handled and stored safely and properly at the site pharmacy or other designated location, and kept in a secured location to which only the Study pharmacist and staff, site Investigator and designated staff have access. Upon receipt, the study drugs will be stored according to the instructions specified on the drug labels. Storage conditions will be adequately monitored and temperature in the area in which the study drug is stored will be controlled, monitored and recorded, at a minimum on a daily

basis. Appropriate temperature logs will be maintained. For more details, please refer to the Study Medications/Central Pharmacy section of the Manual of Operations.

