## 9.7 Safety Analysis

Secondary analyses to examine long-term safety of AFQ056 in this cohort of young children with FXS will be done as follows. Frequencies of adverse events occurring throughout the entire treatment period (both clinical and laboratory) will be tabulated and compared between the active drug and placebo groups during the placebo-controlled period of the study (8 months) and compared across the entire study duration divided based on treatment-assignment at the time of the AE. **Low frequency AEs occurring in less than 5% of the cohort and those that are not different between the drug and placebo groups by visual inspection will not be analyzed further.** Higher frequency events for which statistical comparison would be possible and that appear to be occurring at different frequencies between the drug and placebo groups for either set of comparator groups will be formally compared statistically using a chi-squared analysis. Longitudinal analyses will be done for AEs occurring more frequently in the AFQ056-treated group to determine if there is an increase over time of treatment in these AEs.

[figure not shown]
AFQ056 for Language Learning in Children with FXS

Version v15

Version date 02/03/2021

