## 9.8 Sample Size and Accrual

Estimated required sample size was calculated for the primary endpoint of language. Data from the observational study of was used, and additional estimates of effect size (no raw data) were from an unpublished pre-post randomized clinical trial (RCT). Winarni et al. extracted data from chart reviews for 45 FXS children age 12-50 months. Eleven children were treated with sertraline, and the remainder of 34 were not. Variance components of the random effects and error were estimated and sample size was computed using analytic formulas for LMMs. Recall that in the LMM of Equation 1,  $\gamma_1$  is the difference of the slopes, and it is defined as the proportionate increase of the PL slope,  $\beta_1$ , due to the efficacy of TX (if there is any). We write,  $\gamma_1 = \pi\beta_1$ , where  $\pi$  is the *effect proportion*. For example, if  $\pi = 1$ , Equation 1a shows that the TX slope is twice the PL slope, because  $\beta_1 + \gamma_1 = \beta_1 + (1)\beta_1 = 2\beta_1$ . The analysis used the expressive language and receptive language subscales (age-equivalent scores) of the Mullen Scales of Early Learning. The effect proportion ( $\pi$ ) was estimated considering the on-sertraline group ( $N = 11$ ) as a proxy for TX, and the off-sertraline group ( $N = 34$ ) as a proxy for PL. The effect proportion was also estimated using slope estimates from unpublished data in a RCT of sertraline efficacy. The RCT used a pre-post design over 6 months to study the effect of sertraline versus placebo with FXS children with enrolled age of 24-72 months. Estimates of the effect proportion for the Winarni et al. data were  $\hat{\pi} = 1.27, 2.66$  for expressive language and receptive language respectively, and the estimates from the clinical trial were  $\hat{\pi} = 1.43, 1.52$ . For the analysis, power was set to 80%, and Type I error rate ( $\alpha$ ) was determined as the following. Because this is a proof-of-concept (Phase IIa) proposal with a novel design for a critical population (children with FXS), the  $\alpha$ -level was set to allow for a sensitive detection of efficacy, defined as  $\Delta AIC > 0$  (see statistics section above). It can be shown that  $\Delta AIC = \chi^2_1 - 2$ , so that using  $\chi^2_{1,1-0.16}$  as a critical value for the LRT will allow for detection of  $\Delta AIC > 0$ . In addition to  $\alpha = 0.16$ , sample size was calculated with  $\alpha = 0.10$  because this level is often used in Phase II studies. Figure 3 shows the function of  $\pi$  and  $\alpha$ . A filled circle indicates the required  $N$  for the smallest effect proportion among the studies,  $\min(\hat{\pi}) = 1.43, 1.27$  (expressive, receptive). The figure shows that for the combination of the smallest effect proportion ( $\hat{\pi} = 1.27$ ) and the smallest  $\alpha$ , the required single-arm  $N = 50$  (expressive language). We consider this to be an upper bound on the required sample size, so that a total of  $N = 100$  (50 in each group) should be more than sufficient to detect any magnitude of efficacy (i.e.,  $\Delta AIC > 0$ ). Because of high parental motivation, the dropout rate is anticipated to be very low. However, the  $\alpha = 0.16$  panel of the figure indicates that with total  $N = 100$ , power will still be sufficient to detect  $\Delta AIC > 0$  with as much as 20% dropout ( $100 - 0.2 \times 100 = 80$  or 40 in each group for expressive language).

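### Section 9.5.3 asks whether adverse-event counts are statistically equivalent to placebo, but gives no margin or equivalence test and extends the question to a phase with no placebo group

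*Combined protocol and SAP*

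**What the plan says.** Section 9.5.3 (Safety Endpoints) tracks the numbers of AEs and SAEs over time and then states the purpose of the comparison: "Counts will be statistically compared among the AFQ056 and placebo groups to evaluate safety in regards to whether levels are statistically equivalent over time". It continues: "This will be looked at separately during the main study phase and extended study phase". The list that follows says that clinically significant laboratory values and AEs are "tabulated for descriptive comparison between the placebo and active drug groups". The synopsis says the same.

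Section 9.7 describes the analysis. Frequencies are tabulated and compared between arms over the 8-month placebo-controlled period, and also "compared across the entire study duration divided based on treatment-assignment at the time of the AE". Events in under 5% of the cohort are dropped, and "those that are not different between the drug and placebo groups by visual inspection will not be analyzed further". Events that remain and appear to differ "will be formally compared statistically using a chi-squared analysis".

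Section 5.2 fixes what is taken in the extension: "From the month 8 visit on, study drug will no longer be blinded and all subjects will receive active drug". Section 3 agrees.

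Neither 9.5.3 nor 9.7 gives a margin, an alpha, a confidence level or an equivalence procedure for safety.

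**The concern.** An equivalence conclusion needs a margin fixed in advance and a test, or a confidence interval, set against it. Section 9.5.3 states an equivalence question. Section 9.7 supplies a test of the opposite null hypothesis, and runs it only on events that already look different. The two sections do not fit together, and within 9.5.3 the aim is both inferential and descriptive.

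The extension is a separate problem that needs no power argument. With all children on AFQ056 from month 8, a comparison labelled AFQ056 versus placebo can only contrast the arms as randomised. For a full-length extension that is months 8 to 16 of exposure against months 0 to 8. Similar counts there would not show that the drug resembles placebo. The whole-study comparison by treatment at the time of the event does not repair this, because after month 8 it adds active-drug time only and is no longer a randomised contrast.

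What is at stake is the wording of the safety conclusion. Section 1.3.1 aims to demonstrate long-term safety and tolerability. Sections 2.1 and 9.3 say that extended safety data in young children do not exist and that this trial will help to supply them. An unsupported statement of equivalence would carry weight.

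**Working it through.** **Inputs from the documents.** 100 children randomised 1:1, so 50 per arm (Sections 3 and 9.8). Up to 20% dropout is considered in 9.8, giving 40 per arm. In Table 4 (adults and adolescents, 12 weeks) the highest placebo rate for any single AE is 9.3% (nasopharyngitis, 8/86), and the rate for any AE is 61.6% (53/86).

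**Assumption.** No alpha is stated for safety. Two-sided 0.05 is used, with 0.10 and 0.16 shown because 9.8 uses those for the language endpoint.

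**The plan's own figures.** The 50 per arm comes from the language endpoint and cannot be reproduced, because the variance components are not given and Figure 3 is not shown. The 0.16 level does reproduce: P(chi-squared on 1 df > 2) = 0.157. The dropout arithmetic is also right: 100 − 20 = 80, or 40 per arm. There is no sizing for safety to reproduce.

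**Power of the chi-squared test to detect a doubled risk.** With placebo risk p₁, drug risk p₂ = 2p₁ and mean risk p̄, the normal approximation is

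Φ{ [ (p₂ − p₁) − z·√(2p̄(1−p̄)/n) ] / √[ (p₁(1−p₁) + p₂(1−p₂))/n ] }.

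For 10% versus 20% with n = 50: (0.10 − 1.96 × 0.0714)/0.0707 = −0.565, so power is 0.29. Exact enumeration of the two binomials (uncorrected chi-squared, 50 per arm) gives 0.30. The exact probabilities of missing the doubling are:

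| Placebo → drug risk | alpha 0.05 | alpha 0.10 | alpha 0.16 |
|---|---|---|---|
| 5% → 10% | 86% | 73% | 67% |
| 10% → 20% | 70% | 60% | 50% |
| 15% → 30% | 56% | 43% | 35% |
| 20% → 40% | 41% | 28% | 21% |

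By the approximation, a doubling is more likely missed than found when the placebo risk is below 17.1% (alpha 0.05), 13.1% (0.10) or 10.1% (0.16). Every single AE in Table 4 lies below all three, though 8-month rates in young children may be higher. With 40 per arm at alpha 0.05, the first two rows become 85% and 75%.

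**What identical observed rates would exclude.** For 5/50 versus 5/50 the Wilson limits are 4.3% and 21.4%. Newcombe's interval for the difference is 0 ± √[(0.100 − 0.043)² + (0.214 − 0.100)²] = ±12.7 percentage points. Identical observed rates would still be compatible with an excess of nearly 13 points.

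**Total counts.** For a doubled rate, with mean m events per placebo child and dispersion k, the variance of the log rate ratio is [(1/m + k) + (1/(2m) + k)]/50, and power is Φ(ln 2/√variance − 1.96).

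- m = 0.1: 24% (k = 0, Poisson), 22% (k = 1)
- m = 0.5: 81%, 59%
- m = 1: 98%, 75%

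Under a Poisson assumption the 61.6% any-AE rate implies −ln(1 − 0.616) = 0.96 events per patient in 12 weeks. If that carried over to these children, a doubling of total AE counts would probably be detected.

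**The case against.** The strongest reply is that no equivalence claim is actually planned. A reader might infer that a doubled risk would usually be reported as equivalent, but nothing in the documents says that a non-significant result will be called equivalence. Section 9.5.3 and the synopsis also describe a descriptive comparison. Section 1.3.1 expects a side-effect profile relative to placebo like that of earlier studies, and those showed more dizziness, insomnia, headache, decreased appetite and vomiting on drug (Section 2.2). This stands, and the inference is not made here.

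The quoted sentence is also about counts, whereas the low power concerns proportions with uncommon events. For total counts at plausible rates the test is adequate. This stands too and limits the point to SAEs and uncommon single AEs.

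A reader might further infer that safety will be decided by this comparison. It will not. Safety during the trial rests on the monitoring board and medical monitor (9.9), the trial-stopping rule (6.2.3) and the individual discontinuation criteria (Section 8). Those govern conduct, however, and not the inference reported at the end.

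On the extension, Section 9.6.1 uses the arm labels for the randomised groups while both take drug, so 9.5.3 may mean the same. That makes the comparison intelligible, but it is still not drug versus placebo. The 8–16 versus 0–8 month contrast applies only to full-length extensions, since later enrolees have a shortened one or none.

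The opening of Section 9 promises a formal analysis plan, which could add a margin. The present text does not contain one.

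**Conclusion.** The point holds in limited form. The stated aim of equivalence has no margin and no equivalence test, conflicts with the descriptive wording beside it, and is paired with a difference test run after a 5% and visual-inspection filter. With 50 per arm, a non-significant result cannot support equivalence for SAEs or uncommon single AEs: at an assumed two-sided 0.05, doublings from 5% and 10% are missed in about 86% and 70% of trials. The figures depend on that assumed alpha; at 0.16 they are about 67% and 50%. They do not extend to AEs with placebo risk of about 20% or more, or to total counts of about 0.5 or more events per child. The absence of a placebo group after month 8 holds without any assumption.

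This is a reporting defect on an other-secondary endpoint, minor to moderate in weight, and worth correcting because the remedy is cheap.

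**What to change.** In Section 9.5.3, delete the reference to statistical equivalence. For the 8-month blinded phase, report the AFQ056-minus-placebo risk difference with a 95% confidence interval for any AE, any SAE and each AE, with rate ratios for counts, and make no equivalence statement. For the extension, report AEs descriptively by randomised arm and time since first AFQ056 dose, with no placebo comparison. Bring Section 9.7 into line, so that the 5% and visual-inspection filter does not decide which events receive an interval.

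Keeping an equivalence aim would need a justified margin, and the sample size would limit it. With 50 per arm and truly equal 10% risks (standard error of the difference √(2 × 0.1 × 0.9/50) = 0.06), two one-sided tests using a 90% interval have power 2 × Φ(margin/0.06 − 1.645) − 1. That is 2%, 61% and 91% for margins of 10, 15 and 20 points. These margins are illustrative only.

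The cost is one paragraph of wording plus the matching edit to 9.7. Conduct, data collection and sample size do not change. The trial gives up an equivalence statement that it could not support.
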